5.8.2 Procedures for discontinuation of a subject from investigational product

A subject that discontinues will always be asked about the reason(s) for discontinuation and the presence of any AEs. The Principal Investigator/sub-investigator will perform the best possible observation(s), test(s) and evaluation(s) as well as give appropriate medication and all possible measures for the safety of the subject. They will also immediately inform AstraZeneca of the withdrawal. AEs will be followed up (See Sections 6.4.3 and 6.4.4); diary, glucometer and study drug should be returned by the subject.

Randomised subjects

Randomised subjects who discontinue the study treatment before Week 24 should return and complete the procedures described for Visit 13 as soon as possible but at the latest 7 days after discontinuation. These subjects should also be scheduled for a follow-up visit (ie, procedures of Visit 14) three weeks after discontinuation of investigational product. In addition subjects who discontinue the study due to an AE including a laboratory abnormality should be followed by the investigator until the event has been resolved or stabilised.

After discontinuation of investigational product alternative anti-diabetic treatment will be initiated according to the investigator's judgement and according to local medical practice.

Subjects with an increased CK >10X ULN will have their investigational product held and repeated CK test preferably within 24 hours, but not exceeding 72 hours. If repeated CK is still >10X ULN the subject should permanently discontinue all study medication and be withdrawn from the study (in which case an Adverse Event must be reported). Otherwise investigational product may be resumed unless otherwise contraindicated.

Subjects with increased liver function tests as defined in Section 5.8.1 under listing No.13 will be scheduled for a follow-up visit within 3 days following the receipt of the result. Subjects may remain on study medication until the confirmatory results are obtained. If repeat liver function tests still are increased as outlined in Appendix G the subject should permanently discontinue study medication and be withdrawn from the study (see Appendix G for further guidance).

5.9 Withdrawal from study

Subjects are at any time free to withdraw from study (investigational product and assessments), without prejudice to further treatment (withdrawal of consent). Such subjects will always be asked about the reason(s) and the presence of any AEs. If possible, they will be seen and assessed by an investigator. AEs will be followed up (See Sections 6.4.3 and 6.4.4); diary, glucometer and all study drugs should be returned by the subject.

6. COLLECTION OF STUDY VARIABLES

6.1 Recording of data

The Rave Web Based Data Capture (WBDC) system will be used for data collection and query handling. The investigator will ensure that data are recorded on the eCRF as specified in the study protocol and in accordance with the instructions provided.

The investigator ensures the accuracy, completeness and timeliness of the data recorded and of the provision of answers to data queries. The investigator will sign the completed eCRF. A copy of the completed eCRF will be archived at the study site.

The Principal Investigator/sub-investigator will record data on the observations, tests and assessments specified in the protocol on the eCRFs provided by AstraZeneca. The eCRF will be accompanied with ‘Instructions for the Investigator’, which should be followed. These instructions provide guidance for the recording of study data in the eCRF including how to change data incorrectly recorded.

6.2 Data collection and enrolment

For full details please see the study plan ([Table 2](#)).

6.2.1 Follow-up procedures

A follow-up (Visit 14) will be performed 3 weeks (± 3 days) after the end of the double-blind treatment period, see [Table 2](#) for further details.

6.3 Efficacy

6.3.1 Efficacy laboratory variables

The laboratory parameters that will be measured to assess efficacy are displayed in [Table 6](#) by visit. The results from baseline and onwards will not be reported to the investigator unless FPG value is above 270 mg/dL (15 mmol/L) from Week 0 (Visit 6) to Week 4 (Visit 8), above 240 mg/dL (13.2 mmol/dL) from Week 4 (Visit 8) to Week 12 (Visit 10) and above 200 mg/dL (11.1 mmol/L) from Week 12 (Visit 10) to Week 24 (Visit 13), except for TC, HDL-C, LDL-C and TG which will be reported.

Table 6 Efficacy laboratory variables

Visit	1	2	3	4	5	6	7	8	9	10	11	12	13	14
Study week	-12 or -6	-10	-7	-4	-1	0	1	4	8	12	16	20	24	27
HbA1c	X				X	X		X	X	X	X	X	X	X
FPG	X	X	X	X	X	X	X	X	X	X	X	X	X	X
Insulin	X					X			X		X		X	
C-peptide	X					X			X		X		X	
Glycoalbumin	X					X		X	X	X	X	X	X	

Table 6 Efficacy laboratory variables

Visit	1	2	3	4	5	6	7	8	9	10	11	12	13	14
Study week	-12 or -6	-10	-7	-4	-1	0	1	4	8	12	16	20	24	27
TC						X								X
LDL-C						X								X
HDL-C						X								X
TG						X								X
FFA						X								X

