The subjects who received ongoing medical treatment for diabetes within 6 weeks of enrolment, except for thiazolidinedions (TZD) (a single oral anti-diabetic agent or two agents with less than half of the approved maximal dose for each agent) need a 6-week wash-out period before a 4-week placebo lead-in period.

Outcome variable(s):

Efficacy

Primary outcome variables:

- Change from baseline in HbA1c at 24 weeks

Key secondary outcome variables:

- Change from baseline in FPG at 24 weeks
- Change from baseline in total body weight at 24 weeks

Other secondary outcome variables:

- Percent change from baseline in total body weight at 24 weeks
- Change from baseline in seated SBP at 24 weeks (only subjects with baseline seated SBP ≥ 130)
- Change from baseline in total body weight at 24 weeks (only subjects with baseline BMI ≥ 25 kg/m²)
- Change from baseline in HbA1c at 24 weeks (only subjects with baseline HbA1c $\geq 7.5\%$)
- Proportion of subjects achieving a therapeutic glyceemic response, defined as HbA1c $< 6.5\%$, at 24 weeks
- Proportion of subjects achieving a therapeutic glyceemic response, defined as HbA1c $< 7\%$, at 24 weeks in subjects with baseline HbA1c $\geq 7\%$
- Change from baseline in seated SBP at 24 weeks
- Proportion of subjects with baseline elevated BP who achieve a seated BP of $< 130/80$ mmHg at 24 weeks
- Change from baseline in waist circumference at 24 weeks

- Proportion of subjects discontinued for lack of efficacy or rescued for failing to maintain FPG
- Percent change from baseline in fasting lipids (TC, LDL-C, HDL-C and TG) at 24 weeks
- Change from baseline in fasting insulin and C-peptide at 24 weeks
- Change from baseline in glycoalbumin at 24 weeks

Safety

- AEs and Serious adverse events (SAEs)
- Hypoglycemic events
- Safety Laboratory values
- ECG
- Vital Signs (pulse and BP)
- eGFR
- Physical examination

Statistical methods

For the primary variable, the change from baseline in HbA1c to Week 24, each pair wise treatment group comparison will be tested at a significance level of approximately 0.027, according to Dunnett's method, in order to maintain an overall Type I error rate <0.050 for the primary objective. A hierarchical closed testing procedure will be used to control the Type I error rate across the primary and key secondary objectives within each dapagliflozin treatment group.

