Fasting serum lipids: TC, LDL-C, HDL-C, TG, and FFA						X							X	
Hepatitis Screen Panel ^c , TSH, and PT/PTT	X													
Cystatine C						X							X	
Parathormone (PTH)						X							X	X

Table 2 Study plan

Procedure	Screening Period	Wash-out Period ^a		Lead-in Period		Double-blind, Placebo-controlled Treatment Period								Follow-up Period
	Wk -12 or Wk -6 ^a	Wk -10	Wk -7	Wk -4	Wk -1	Wk 0	Wk 1 ^b	Wk 4 ^b	Wk 8 ^b	Wk 12 ^b	Wk 16 ^b	Wk 20 ^b	Wk 24	Wk 27
Visit	1	2	3	4	5	6	7	8	9	10	11	12	13	14
Visit window (days)	+7	±3	±3	±3	±3	0	±3	±3	±3	±3	±3	±3	±3	±3
Clinical Drug Supplies														
Dispense Study Medication				X		X		X	X	X	X	X	X	
Review Medication Compliance					X	X	X	X	X	X	X	X	X	X

FFA: free fatty acid, TSH: thyroid stimulating hormone, PT: prothrombin time, PTT: partial thromboplastin time, WOCBP: Women of child bearing potential

- a Wash-out period is applicable only for subjects with ongoing treatment with anti-diabetic agents. For treatment-naïve subjects, screening period is Week -6 to -4.
- b Subjects not completing the treatment period should complete the procedures described for Visit 13 within 7 days after discontinuation. These subjects should also complete the procedures described for a follow-up visit (ie, Visit 14) three weeks after discontinuation of investigational product.
- c Includes anti-HAV (IgM, IgG), HBsAg, anti-HBc (igG, IgM) and anti-HCV.

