6.5 Patient reported outcomes (PRO) – Not applicable

6.6 Pharmacokinetics – Not applicable

6.7 Pharmacodynamics – Not applicable

6.8 Pharmacogenetics – Not applicable

6.9 Health economics – Not applicable

7. BIOLOGICAL SAMPLING PROCEDURES

7.1 Volume of blood

The total volume of blood that will be drawn from each subject in this study is as follows:

Table 8 Volume of blood to be drawn from each subject (mL)

Visit	1	2 ^a	3 ^a	4	5	6	7	8	9	10	11	12	13	14	Maximum volume
Sample volume	26	2	2	13.5	5	21.5	13.5	16.5	16.5	16.5	16.5	16.5	21.5	13.5	201

a Only for subjects who received ongoing medical treatment for diabetes within 6 weeks of enrolment, except for TZD (a single oral anti-diabetic agent or two agents with less than half of the approved maximal dose for each agent)

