12.2.2.3 Other secondary efficacy variables

The following variables, except for the percent changes from baseline in lipids and body weight, will be analysed based on similar ANCOVA model as the primary efficacy analysis described in Section [12.2.2.1](#). The percent changes from baseline to Week 24 (LOCF) in lipids (TC, LDL-C, HDL-C and fasting TG) and body weight will be analysed on a log scale in an ANCOVA model with terms similar to the primary efficacy analysis.

- the percent change from baseline in total body weight at Week 24 (LOCF)

- the change from baseline in seated SBP in subjects with baseline seated SBP ≥ 130 mmHg at Week 24 (LOCF)
- the change from baseline in total body weight in subjects with baseline BMI ≥ 25 kg/m² at Week 24 (LOCF)
- the change from baseline in HbA1c at Week 24 (LOCF) in subjects with baseline HbA1c $\geq 7.5\%$
- the change from baseline in seated SBP at Week 24 (LOCF)
- the change from baseline in waist circumference at Week 24 (LOCF)
- the percent change from baseline in fasting lipids (TC, LDL-C, HDL-C and TC) at Week 24 (LOCF)
- the change from baseline in fasting insulin and C-peptide at Week 24 (LOCF)
- the change from baseline in glicocalbumin at Week 24 (LOCF)

For the following proportions, estimates, confidence intervals, and tests will be obtained using the methodology of Zhang, Tsiatis and Davidian ([Zhang M et al 2007](#)) and Tsiatis, Davidian, Zhang and Lu ([Tsiatis A et al 2007](#)) with adjustment for gender and baseline variable (eg, adjustment for baseline HbA1c). For each treatment group, the probability of response is first modeled using a logistic regression model with gender and baseline (eg, baseline HbA1c) as the covariate. Treatment group estimates of response rate are then obtained by integrating each group's modeled probability of response over the observed distribution of baseline covariate (combined across groups). The difference in response rate between each of the dapagliflozin treatment groups and the placebo group will be displayed along with the 95% confidence intervals. Nominal p-values for the difference between the dapagliflozin treatment groups versus placebo will be provided (if applicable). When there are less than 5 responders on average by treatment group, the unadjusted (and difference) proportions, exact 95% confidence interval, and p-values from the Fisher's exact test (when applicable) will be provided.

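### Table 6 puts the only post-baseline lipid sample at Week 27, off drug, while Table 2 and the endpoint need it at Week 24

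*Protocol*

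**What the plan says.** Two protocol tables schedule the same fasting lipid samples.

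- **Table 6 (Section 6.3.1).** The text introduces it with "The laboratory parameters that will be measured to assess efficacy are displayed in" Table 6, by visit. All five lipid rows (TC, LDL-C, HDL-C, TG, FFA) are marked at Visits 6 and 14. Visit 13 is blank.
- **Table 2 (study plan, after Section 3.1.5).** The row "Fasting serum lipids: TC, LDL-C, HDL-C, TG, and FFA" is marked at Visits 6 and 13. Visit 14 is blank.

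The endpoint is fixed at Week 24. The synopsis lists "Percent change from baseline in fasting lipids (TC, LDL-C, HDL-C and TG) at 24 weeks", and Section 12.2.2.3 analyses "The percent changes from baseline to Week 24 (LOCF) in lipids" by ANCOVA on the log scale. (The bulleted list in that section prints TC twice where the synopsis has TG; I read it as TG.)

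Three other provisions bear on the point. Section 3.1.5 stops study drug at Visit 13 and lets subjects take other anti-diabetic drugs openly during follow-up. Section 6.2.1 places Visit 14 three weeks, plus or minus 3 days, after the end of double-blind treatment. Section 11.1.2 defines LOCF as looking back from the time point to an earlier post-baseline value.

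**The concern.** The two schedules cannot both be followed. Because each contains a single post-baseline lipid sample, the choice between them decides whether the Week 24 endpoint exists at all. A laboratory or site that builds its kits from the efficacy table would draw lipids three weeks after the last dose, possibly on another anti-diabetic drug, and would draw none at the end of treatment. A missed fasting sample cannot be recovered afterwards, and no analysis method can replace it.

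**Working it through.** **1. Marks by column.** Both tables have 14 visit columns. Counting the cells in each row gives:

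| Row | Table | Marked visits |
|---|---|---|
| TC (LDL-C, HDL-C, TG, FFA laid out identically) | 6 | 6, 14 |
| Fasting serum lipids | 2 | 6, 13 |
| HbA1c (check row) | 6 | 1, 5, 6, 8, 9, 10, 11, 12, 13, 14 |
| Insulin (check row) | 6 | 1, 6, 9, 11, 13 |
| PTH (check row) | 2 | 6, 13, 14 |

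Every row counted has exactly 14 cells. The Table 6 check rows agree with Table 2. Only the second lipid mark differs.

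**2. What Table 6 leaves for the analysis.** For a subject who completes treatment:

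- lipid values at Week 0: one (baseline);
- lipid values after Week 0 and up to Week 24: none;
- lipid value at Week 27: one, at least 21 − 3 = 18 days after the end of treatment.

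The Week 24 value is not observed. LOCF needs a post-baseline value before Week 24, and there is none. The Week 27 value comes after the time point, so the rule in Section 11.1.2 cannot use it.

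A subject who stops early has the Visit 14 procedures three weeks after stopping (Section 5.8.2), so under Table 6 might have a lipid value before Week 24. That value is off drug. Under Table 6, the only values LOCF could use would therefore come from early discontinuers, after they had stopped treatment.

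**3. Size.** The variables affected are TC, LDL-C, HDL-C and TG: 4 variables, each compared with placebo for 2 doses, so 4 × 2 = 8 nominal comparisons. Planned randomisation is 3 × 85 = 255 subjects. Under Table 6, 100% of completers lack all four Week 24 values; under Table 2, 0% do so by design.

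**4. Blood volumes (Table 8).** First the stated total:

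26 + 2 + 2 + 13.5 + 5 + 21.5 + 13.5 + (5 × 16.5) + 21.5 + 13.5 = 201 mL, as stated.

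The sum does not itself show when lipids are drawn. The visit volumes help a little:

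- Visit 6, where both tables place lipids: 21.5 mL.
- Visit 13: 21.5 mL. Under Table 2 its blood tests are the same as at Visit 6.
- Visit 14: 13.5 mL, equal to Visits 4 and 7, which have no lipids in either table.

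This pattern fits Table 2. It also shows that 21.5 mL is enough for the Visit 13 list with lipids, since the same list is covered by 21.5 mL at Visit 6.

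**The case against.** **The mark may have moved when the table was read from PDF.** The lipid rows sit in a continuation of Table 6, whereas the Table 6 check rows are in its first part, and a common fault could shift all five rows together. The continuation of Table 7 also departs from Table 2, with a Visit 10 mark for spot-urine sodium and glucose, and the text alone does not show why. This cannot be fully excluded. But the Visit 6 mark in the same five rows agrees with Table 2, and the rows still have 14 cells. An artefact would have to insert one empty cell between the marks and drop one at the end, in each of the five rows. A look at the original page settles it.

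**The protocol says which table leads.** Section 6.2 reads "For full details please see the study plan", meaning Table 2, and Section 6.2.1 sends the reader there for Visit 14. A site working from Table 2 would draw lipids at Week 24. This stands: the complete loss is what happens if Table 6 is followed, not a forecast. It does not make Table 6 correct, since Section 6.3.1 presents that table as the efficacy sampling schedule.

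**Table 8 is weak evidence.** Visit 14 includes HbA1c and PTH, which Visit 7 lacks, at the same 13.5 mL. Visit 9 adds insulin and C-peptide to Visit 8 at an unchanged 16.5 mL. The extra 5 mL at Visits 6 and 13 could be for cystatin C and PTH. This also stands: Table 8 is consistent with Table 2 but does not prove it.

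**Lipids are a minor endpoint.** They are supportive variables tested at a nominal 0.05, outside the hierarchical procedure (Section 12.2.2). That limits the consequence, not the error.

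**An amendment may have corrected it.** The part of Amendment 1 that is available revises the text of Section 6.3.1 and still refers to Table 6. The other amendment pages are not available, so a correction elsewhere cannot be ruled out.

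**Conclusion.** The contradiction is real, and Table 6 is wrong as written. The objectives, the outcome list, the analysis section and the study plan all require lipids at Week 24; only Table 6 places them at Week 27. Followed literally, Table 6 removes the four lipid endpoints for every completer among up to 255 subjects. The primary analysis, the key secondary analyses, the sample size and the type I error control are untouched.

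The conclusion assumes that the table marks were read in their true columns and that no correction exists in the amendment pages not available. The size of the loss is conditional on Table 6 being the schedule used. The reason to correct it before sampling is that the loss would be irreversible while the correction is almost free.

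**What to change.** In Table 6, move the second mark in the TC, LDL-C, HDL-C, TG and FFA rows from Visit 14 (Week 27) to Visit 13 (Week 24), so that it agrees with Table 2. Confirm the column positions against the original page first. Then check that the laboratory manual and the central laboratory's kits provide for lipids at Visit 13, before any subject reaches that visit.

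The cost is a table correction and a kit check. No visit is added, and Table 8 needs no change because Visit 13 already allows 21.5 mL. The repeated TC in the Section 12.2.2.3 list can be corrected to TG at the same time.

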6.3.2 HbA1c

HbA1c is the primary assessment for the determination of glycemic efficacy accepted referred by the [Japanese Guideline on Clinical Evaluation methods on Oral Hypoglycemic Agents](#). HbA1c will be analysed by a central laboratory according to the procedures described in the Laboratory Manual which will be distributed to each study site during site initiation. The measurement of HbA1c is NGSP.

6.3.3 FPG

FPG is a well established measure of glycemic efficacy and considered to be an acceptable secondary endpoint.

6.3.4 Weight and height

The subject's weight will be recorded in kilogram (kg) to one decimal place, on a fasting stomach with light clothing and no shoes. The subject's height will be recorded in centimetres, with no shoes. All readings should be recorded as accurately as possible and the same scale should be used for all assessments for a given subject.

6.3.5 BMI

BMI is a calculated ratio between weight and height ($\text{weight} / \text{height}^2$, where weight is measured in kg, and height in metres) and will be computed by AstraZeneca.

6.3.6 Blood pressure

As BP is both an efficacy and safety variable in this study, measurement of BP is described in Sections [6.4.8.1](#) and [6.4.8.2](#).

6.3.7 Waist circumference

The waist circumference should be measured in the standing position at the natural waist (smallest waist circumference). If there is no natural waist, the measurement should be made at the level of the umbilicus. Measurements should be made at the end of a normal inspiration.

6.3.8 Glycoalbumin

Glycoalbumin is a well established measure of glycemic efficacy and considered to be an acceptable secondary endpoint.

6.4 Safety

The Principal Investigator is responsible for ensuring that all staff involved in the study is familiar with the content of this section.

6.4.1 Definition of adverse events

An adverse event is the development of an undesirable medical condition or the deterioration of a pre-existing medical condition following or during exposure to a pharmaceutical product, whether or not considered causally related to the product. An undesirable medical condition can be symptoms (eg, nausea, chest pain), signs (eg, tachycardia, enlarged liver) or the abnormal results of an investigation (eg, laboratory findings, electrocardiogram). In clinical studies, an AE can include an undesirable medical condition occurring at any time, including run-in or washout periods, even if no study treatment has been administered.

The term AE is used to include both serious and non-serious AEs.

For cases where it could be suspected that a tissue-derived medicine has been contaminated by a pathogen, information about any of the above conditions (including infection) should be collected.

6.4.2 Definitions of serious adverse event

A SAE is an AE occurring during any study phase (ie, run-in, treatment, washout, follow-up), that fulfils one or more of the following criteria:

- Results in death
- Is immediately life-threatening
- Requires in-subject hospitalisation or prolongation of existing hospitalisation (including hospitalisation for tests related to AEs), except hospitalisation that has been planned before enrolment
- Results in persistent or significant disability or incapacity
- Is a congenital abnormality or birth defect
- Is an important medical event that may jeopardise the subject or may require medical intervention to prevent one of the outcomes listed above.
- Cancer
- Drug Dependency/ abuse

- Overdose (defined as the accidental or intentional ingestion of any dose of the investigational product that is considered both excessive and medically important)

For further guidance on the definition of a SAE, see Appendix B to the Clinical Study Protocol.

6.4.3 Recording of adverse events

Time period for collection of adverse events

AEs will be collected from the start of the placebo lead-in period (Visit 4 to 5) throughout the treatment period (Visit 6 to 13) and including the follow-up period (Visit 14).

SAEs will be recorded from the time of informed consent is obtained until the end of the study (Visit 14).

Follow-up of unresolved adverse events

Any AEs that are unresolved at the end of the study (Visit 14) or at discontinuation visit in the study are followed up by the investigator for as long as medically indicated, but without further recording in the eCRF. AstraZeneca retains the right to request additional information for any subject with ongoing AE(s)/SAE(s) at the end of the study, if judged necessary.

Variables

The following variables will be collect for each AE;

- AE (verbatim)
- the date when the AE started and stopped
- maximum intensity
- whether the AE is serious or not
- investigator causality rating against the Investigational Product (yes or no)
- action taken with regard to investigational product
- outcome.

In addition, the following variables will be collected for SAEs:

- Date AE met criteria for serious AE
- Date Investigator became aware of serious AE
- AE is serious due to
- Date of hospitalisation

- Date of discharge
- Probable cause of death
- Date of death
- Autopsy performed
- Causality assessment in relation to Study procedure(s)
- Causality assessment in relation to Other medication
- Description of AE

Maximum intensity will be graded according to the following definitions:

- mild (awareness of sign or symptom, but easily tolerated)
- moderate (discomfort sufficient to cause interference with normal activities)
- severe (incapacitating, with inability to perform normal activities)
- very severe (debilitating, significantly incapacitates subject despite symptomatic therapy)

It is important to distinguish between serious and severe AEs. Severity is a measure of intensity whereas seriousness is defined by the criteria in Section 6.4.2. An AE of severe intensity need not necessarily be considered serious. For example, nausea that persists for several hours may be considered severe nausea, but not a SAE. On the other hand, a stroke that results in only a limited degree of disability may be considered a mild stroke but would be a SAE.

Causality collection

The Investigator will assess causal relationship between Investigational Product and each AE, and answer ‘yes’ or ‘no’ to the question ‘Do you consider that there is a reasonable possibility that the event may have been caused by the investigational product?’

For SAEs causal relationship will also be assessed for other medication and study procedures and additional study drug (rescue medication). Note that for SAEs that could be associated with any study procedure the causal relationship is implied as ‘yes’.

A guide to the interpretation of the causality question is found in Appendix B to the Clinical Study Protocol.

Adverse Events based on signs and symptoms

All AEs spontaneously reported by the subject or reported in response to the open question from the study personnel: ‘Have you had any health problems since the previous visit/you were last asked?’, or revealed by observation will be collected and recorded in the eCRF. When collecting AEs, the recording of diagnoses is preferred (when possible) to recording a list of signs and symptoms. However, if a diagnosis is known and there are other signs or symptoms that are not generally part of the diagnosis, the diagnosis and each sign or symptom will be recorded separately.

Adverse Events based on examinations and tests

Deterioration as compared to baseline in protocol-mandated laboratory values, vital signs and other safety variables will only be reported as AEs if they are clinically significant, fulfil any of the SAE criteria or are the reason for discontinuation of treatment with the investigational product, or require the subject to receive specific corrective therapy. If a deterioration in a laboratory value/vital sign is associated with clinical signs and symptoms, the sign/symptom will be reported as an AE and the associated laboratory result/vital sign will be considered as additional information. Any new or aggravated clinically relevant abnormal medical finding at a physical examination or ECG evaluation as compared with the baseline assessment will be reported as an AE.

Clinically relevant deterioration in non-protocol-mandated measurements will be reported as AE(s).

Wherever possible the reporting investigator uses the clinical, rather than the laboratory term (eg, anaemia versus low haemoglobin value).

Hypoglycemic events

A separate section in the eCRF will be used to document all reported episodes of hypoglycemia (See Section 6.4.9). Hypoglycemic episodes should only be reported on the AE eCRF page if the event fulfils protocol criteria for a SAE (See Section 6.4.2). In this case, an SAE must be reported in addition to the hypoglycemia eCRF pages for hypoglycemia.

Follow-up of unresolved adverse events

All AEs and SAEs, including those that are ongoing at the end of the study or at discontinuation, will be followed up until resolution or until the Investigator decides that no further follow-up is necessary. AstraZeneca retains the right to request additional information for any subject with ongoing AEs/SAEs at the end of the study, if judged necessary. The requirement to follow-up is not intended to delay database lock or production of the clinical study report. Both these activities should proceed as planned with ongoing AEs if necessary.

Any follow-up of ongoing SAEs after database lock will be reported to AstraZeneca, who will notify the appropriate Bristol-Myers Squibb Pharmacovigilance contact.

Cardiovascular events

Cardiovascular events will be monitored in the study population and an independent cardiovascular adjudication committee will review events. Cardiovascular events will be analyzed in conjunction with cardiovascular events observed in other Phase II and Phase III dapagliflozin studies and reported separately.

